#### **3.1. Analysis Sets**

Analysis sets define the participants to be included in an analysis. Analysis sets and their definitions are provided in this section. The analysis set will be identified and included as a subtitle of each TFLs.

For each analysis set, the number and percentage of participants will be summarized by cohort based on the All Enrolled Analysis Set.

A listing of reasons for exclusion from analysis sets will be provided by participant.

##### **3.1.1. All Enrolled Analysis Set**

All Enrolled Analysis Set includes all participants who were randomized into Cohort 1 or enrolled into Cohort 2. This is the primary analysis set for by-participant listings.

##### **3.1.2. Full Analysis Set (All LEN Analysis)**

The Full Analysis Set (FAS) for the All LEN Analysis includes all participants who are enrolled into the study and receive at least one dose of any LEN.

### **3.1.3. Safety Analysis Set (All LEN Analysis)**

The Safety Analysis Set includes all participants who are enrolled and receive at least one dose of any LEN. This is the primary analysis set for safety analyses. This analysis set will be used to describe baseline information as well as safety summary.

### **3.2. Participant Grouping**

For analyses based on the FAS, participants will be grouped according to the treatment to which they were enrolled. For analyses based on the Safety, and PK Analysis Sets, participants will be grouped according to the actual treatment received.

### **3.3. Strata and Covariates**

This study does not use a stratified randomization schedule when enrolling participants. No covariates will be included in efficacy analyses.

### **3.4. Examination of Participant Subgroups**

#### **3.4.1. Participant Subgroups for Efficacy Analyses**

The proportion of participants with HIV-1 RNA < 50 copies/mL at Week 104 as determined by the United States (US) Food and Drug Administration (FDA)-defined snapshot algorithm {[U. S. Department of Health and Human Services 2015](#)} will be analyzed for the following participant subgroups based on FAS for the All LEN Analysis:

- Age (years): (a) < 50 and (b)  $\geq$  50
- Sex: (a) male and (b) female
- Race: (a) black and (b) nonblack
- Region: (a) US and (b) Ex-US
- Baseline CD4 cell count categories (/ $\mu$ L): (a) < 200 and (b)  $\geq$  200
- Baseline viral load categories (copies/mL): (a)  $\leq$  100,000 and (b) > 100,000
- Baseline INSTI resistance categories: (a) with INSTI resistance and (b) without INSTI resistance
- Genotypic sensitivity score (GSS) based on baseline OBR: eg, 0, 1, 2, etc.
- Phenotypic sensitivity score (PSS) based on baseline OBR: eg, 0, 1, 2, etc.
- Overall susceptibility score (OSS) based on baseline OBR: eg, 0, 1, 2, etc.
- Use of dolutegravir (DTG) and/or darunavir (DRV) in baseline OBR: (a) With DTG and DRV (b) With DTG, without DRV (c) Without DTG, with DRV (d) Without DTG or DRV

- Use of ibalizumab (IMAB) and/or fostemsavir (FTR) in baseline OBR: (a) With IMAB and FTR (b) With IMAB, without FTR (c) Without IMAB, with FTR (d) Without IMAB or FTR (e) With either IMAB or FTR (f) With IMAB, regardless of FTR (g) Without IMAB, regardless of FTR (h) Regardless of IMAB, with FTR (i) Regardless of IMAB, without FTR
- Number of fully active ARV agents from baseline OBR: 0, 1, 2, 2 or more, 3 or more

### **3.4.2. Participant Subgroups for Safety Analyses**

Incidence of all treatment-emergent AEs (TEAEs) will be analyzed for the following participant subgroups using the Safety Analysis Set for All LEN Analysis

- Age (years): (a)  $< 50$  and (b)  $\geq 50$
- Sex: (a) male and (b) female
- Race: (a) black and (b) nonblack
- Region: (a) US and (b) Ex-US

### **3.5. Multiple Comparisons**

No alpha level adjustment is needed as the primary efficacy endpoint was analyzed at the DMC analysis and has been included in the Week 26 CSR.

### **3.6. Missing Data and Outliers**

#### **3.6.1. Missing Data**

In general, missing data will not be imputed unless methods for handling missing data are specified. Exceptions are presented in this document.

For missing last study date, imputation rules are described in Section 4.3. The handling of missing or incomplete dates for AE onset is described in Section 7.1.5.2, and for antiretroviral medications and concomitant medications in Section 7.4.

#### **3.6.2. Outliers**

Outliers will be identified during the data management and data analysis process, but no sensitivity analyses will be conducted. All data will be included in the data analysis.

### **3.7. Data Handling Conventions and Transformations**

Only year of birth is collected in this study. The following conventions will be used for the imputation of full date of birth:

- If year of birth is collected, “01 July” will be imputed as the day and month of birth
- If year of birth is missing, date of birth will not be imputed

In general, age collected at baseline (in years) will be used for analyses and presented in listings. If age at baseline is not available for a participant, age derived based on date of birth and the baseline visit date will be used instead. If an enrolled participant was not dosed with any study drug, the randomization/enrollment date will be used instead of the baseline visit date. For screen failures, the date the first informed consent was signed will be used for the age derivation. Age required for longitudinal and temporal calculations and analyses (eg, estimates of creatinine clearance) will be based on age derived from date of birth and the date of the measurement or event, unless otherwise specified.

Non-PK data that are continuous in nature but are less than the lower limit of quantitation (LOQ) or above the upper LOQ will be imputed as follows:

- A value that is 1 unit less than the LOQ will be used to calculate descriptive statistics if the datum is reported in the form of “< x” (where x is considered the LOQ). For example, if the values are reported as < 50 and < 5.0, values of 49 and 4.9, respectively, will be used to calculate summary statistics. An exception to this rule is any value reported as < 1 or < 0.1, etc. For values reported as < 1 or < 0.1, a value of 0.9 or 0.09, respectively, will be used to calculate summary statistics.
- A value that is 1 unit above the LOQ will be used to calculate descriptive statistics if the datum is reported in the form of “> x” (where x is considered the LOQ). Values with decimal points will follow the same logic as above.
- The LOQ will be used to calculate descriptive statistics if the datum is reported in the form of “≤ x” or “≥ x” (where x is considered the LOQ).

Logarithmic (base 10) transformations will be applied to HIV-1 RNA data for efficacy analysis. HIV-1 RNA results of ‘No HIV-1 RNA detected’ and “<20 cp/mL HIV-1 RNA Detected” will be imputed as 19 copies/mL for analysis purposes.

Natural logarithm transformation will be used for analyzing concentrations and PK parameters. Concentration and PK parameter values that are below the limit of quantitation (BLQ) will be presented as “BLQ” in the data listing. Values that are BLQ will be treated as 0 at predose time points, and one-half the value of the LOQ at postdose time points for summary purposes or statistical model fitting.

The following conventions will be used for the presentation of summary and order statistics for PK concentrations:

- If at least 1 participant has a concentration value of BLQ for the time point, the minimum value will be displayed as “BLQ”.
- If more than 25% of the participants have a concentration data value of BLQ for a given time point, the minimum and Q1 values will be displayed as “BLQ”.
- If more than 50% of the participants have a concentration data value of BLQ for a given time point, the minimum, Q1, and median values will be displayed as “BLQ”.

- If more than 75% of the participants have a concentration data value of BLQ for a given time point, the minimum, Q1, median, and Q3 values will be displayed as “BLQ”.
- If all participants have concentration data values of BLQ for a given time point, all order statistics (minimum, Q1, median, Q3, and maximum) will be displayed as “BLQ”.

### 3.8. Analysis Visit Windows

#### 3.8.1. Definition of Key Dates and Study Day

**First Dose Date** for All LEN Analysis is defined as the earliest dose date of either blinded or open-label oral LEN, as recorded on the Study Drug Administration eCRF form.

**Last Dose Date** for All LEN Analysis is defined for participants who prematurely discontinue study drug in any phase (ie, main phase or extension phase) of the study or who complete study drug as the latest dose date of either blinded or open-label oral LEN or SC LEN.

**First Dose Date** for the study is defined as the day when the first dose of blinded study drug (LEN or Placebo) or open-label oral LEN was taken, as recorded on the Study Drug Administration eCRF form.

**Last Dose Date** for the study is defined for participants who prematurely discontinue study drug in any phase of the study or who complete study drug as the latest dose date of any study drug including blinded study drug, open-label oral LEN, and SC LEN.

**First Dose Date of Oral Bridging** is defined for participants who received oral bridging of LEN as the earliest dose date of oral bridging of LEN, as recorded on the Study Drug Administration - Oral Bridging eCRF form.

**Last Dose Date of Oral Bridging** is defined for participants who received oral bridging of LEN, as the latest dose date of oral bridging of LEN before the First Dose Date of Resumed SC Injection, as recorded on the Study Drug Administration - Oral Bridging eCRF form.

**First Dose Date of Resumed SC Injection** is defined for participants who received oral bridging of LEN and resumed the SC injection, as the earliest dose date of SC LEN following the lifting of the Clinical Hold on SC LEN, as recorded on the Study Drug Administration – SC eCRF form.

**Last Study Date** is defined as the latest date of non-missing clinic visits and/or laboratory visits, and/or AE onset and end dates without any imputation, including the 30, 90, and 180-day follow-up visit dates for participants who prematurely discontinue or complete the study.

**Study Day** will be calculated from the First Dose Date, as defined separately above for All LEN Analysis and for the study, and will be derived as follows:

- For postdose study days: Assessment Date – First Dose Date + 1
- For study days prior to the first dose: Assessment Date – First Dose Date

### 3.8.2. Analysis Visit Windows

For All LEN Analysis, participant’s visits might not occur on protocol-specified visits. Therefore, for the purpose of analysis, observations will be assigned to analysis windows (see Table 3-1).

**Table 3-1. Analysis Windows for All LEN Analysis**

Analysis Visit	Nominal Study Day	Analysis Window Study Day Range	
		HIV-1 RNA and Vital Signs	Hematology, (Urine) Chemistry, Urinalysis, CD4 Cell Count, and CD4%
Baseline		≤ First Dose Date, if time not available ≤ First Dose Date/Time, if time available	≤ First Dose Date, if time not available ≤ First Dose Date/Time, if time available
Day 1 (Postdose) a	1	> First Dose Date/Time, 1	> First Dose Date/Time, 1
Day 2	2	2, 5	NP
Day 8	8	6, 11	2, 11
Day 1 SC	15	12, 29	12, 29
Week 4	43	30, 64	30, 64
Week 10	85	65, 106	65, 106
Week 16	127	107, 148	107, 148
Week 22	169	149, 183	149, 183
Week 26	197	184, 232	184, 232
Week 36	267	233, 323	233, 323
Week 52	379	324, 414	324, 414
Week 62	449	415, 505	415, 505
Week 78	561	506, 596	506, 596
Week 88	631	597, 687	597, 687
Week 104	743	688, 778	688, 778
Week 114	813	779, 869	779, 869
Week 130	925	870, 960	870, 960
Week 140	995	961, 1051	961, 1051
Week 156	1107	1052, 1142	1052, 1142
Week 166	1177	1143, 1233	1143, 1233
Week 182	1289	1234, 1324	1234, 1324
Week 192	1359	1325, 1415	1325, 1415
Week 208	1471	1416, 1506	1416, 1506

NP = Not planned by the protocol

a Day 1 postdose will be used to label the records collected on Day 1 with collection time after the Day 1 dosing time. The Day 1 postdose will be used in listings to identify such records. Day 1 postdose visit will not be included in by-visit table summary

### **3.8.3. Selection of Data in the Event of Multiple Records in an Analysis Visit Window**

Depending on the statistical analysis method, single values may be required for each analysis window. For example, change from baseline by visit usually requires a single value, whereas a time-to-event analysis would not require 1 value per analysis window.

If multiple valid, nonmissing measurements exist in an analysis window, records will be chosen based on the following rules if a single value is needed:

- For baseline, the last nonmissing value with collection date (and time, if available) on or prior to the first dose date (and time) of study drug will be selected, unless specified differently. If there are multiple records with the same time or no time recorded on the same day, the baseline value will be the average of the measurements for continuous data (except for HIV-1 RNA, see below), or the measurement with the lowest severity (eg, normal will be selected over abnormal for safety electrocardiogram [ECG] findings) for categorical data.
- For postbaseline values (ie, data with collection date [and time, if available] after the first dose date [and time] of study drug):
  - The record closest to the nominal day for that visit will be selected with the exception of CD4 cell counts and CD4% in which the latest record will be selected and HIV-1 RNA level (see below).
  - If there are 2 records that are equidistant from the nominal day, the later record will be selected.
  - If there is more than 1 record on the selected day, the average will be taken for continuous data (except for HIV-1 RNA, see below) and the worse severity will be taken for categorical data, unless otherwise specified.
- For baseline HIV-1 RNA, the latest (considering both date and time) record(s) on or prior to the first dose date and time of study drug will be selected. For postbaseline HIV-1 RNA, the latest record(s) on the window will be selected. For both baseline and postbaseline HIV-1 RNA, if both “HIV RNA Taqman 2.0” and “HIV RNA Taqman 2.0 Repeat” or both “HIV RNA COBAS 6800” and “HIV RNA COBAS 6800 Repeat” are available with the same collection time, the results from the “HIV RNA Taqman Repeat” or “HIV RNA COBAS 6800 Repeat” will be selected for analysis purposes; otherwise, if there are multiple “HIV RNA Taqman 2.0” or “HIV RNA COBAS 6800” records with the same collection time, the geometric mean will be taken for analysis purposes.

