6.7.1. Suboptimal Virologic Response

Suboptimal virology response is defined as:

- HIV-1 RNA ≥ 50 copies/mL **and** $< 1 \log_{10}$ HIV-1 RNA reduction from the start of oral LEN (Day 1 for Cohort 1A and Cohort 2 participants, or Day 15 for Cohort 1B participants) at the Week 4 visit.

Following the first instance of SVR at Week 4, participants will be asked to return to the clinic for a scheduled or unscheduled blood draw (2 to 3 weeks after first SVR visit) for confirmation of SVR. A plasma sample from either the first instance or the SVR confirmation visit will be tested for HIV-1 capsid genotypic and phenotypic resistance. In addition, if SVR is confirmed, a plasma sample from the SVR confirmation visit will be tested for HIV-1 PR, RT, and IN genotypic and phenotypic resistance.

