### **3. GENERAL CONSIDERATIONS FOR DATA ANALYSES**

Year 2 and Year 3 Analyses will be based on All LEN Analysis.

All LEN Analysis include data collected from participants who receive at least one dose of LEN (ie, oral LEN [blinded or open-label] or SC LEN). Data collected on and after the first dose of LEN are included in this analysis. Data included in this analysis will be used to assess efficacy, and safety LEN. Results will be summarized by cohort and total, unless specified otherwise.

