#### **7.1.5. Treatment-Emergent Adverse Events**

##### **7.1.5.1. Definition of Treatment-Emergent Adverse Events**

The TEAEs are defined as any AEs that begin on or after the date of first dose of study drug or any AEs leading to premature discontinuation of study drug. For participants who discontinue from the oral bridging of LEN, only AEs collected up to 60 days after the Last Dose Date of Oral Bridging will be considered treatment emergent.

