### 7.2.1. Summaries of Numeric Laboratory Results

Descriptive statistics will be provided by treatment group for white blood cells, neutrophils (absolute result and %), lymphocytes (absolute result and %), creatinine, estimated glomerular filtration rate (eGFR) by CG, albumin, alkaline phosphatase, alanine amino transferase (ALT), aspartate amino transferase (AST), total bilirubin as follows:

- Baseline values
- Values at each postbaseline visit
- Change from baseline at each postbaseline visit

A baseline laboratory value will be defined as the last measurement obtained on or prior to the date of first dose of study drug. Change from baseline to a postbaseline visit will be defined as the visit value minus the baseline value. The mean, median, Q1, Q3, minimum, and maximum values will be displayed to the reported number of digits; SD values will be displayed to the reported number of digits plus 1.

Median (Q1, Q3) of the change from baseline values for the above laboratory tests (except for % neutrophils and lymphocytes) will be plotted using a line plot by cohort and treatment group and visit.

In the case of multiple values in an analysis window, data will be selected for analysis as described in Section 3.8.3.

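### For Cohort 1B, the SAP starts the All LEN analysis at the first LEN dose but ties baseline and treatment-emergence to the first dose of study drug, which includes placebo

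*SAP*

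**What the plan says.** SAP 3 bases the Year 2 and Year 3 analyses on the All LEN Analysis and sets its scope: "Data collected on and after the first dose of LEN are included in this analysis". SAP 3.8.1 then defines two first dose dates. The one for All LEN is the earliest oral LEN dose. The one for the study is "the day when the first dose of blinded study drug (LEN or Placebo) or open-label oral LEN was taken", and the matching last-dose definition lists blinded drug among the study drugs. Study Day is derived separately from each date. Table 3-1, titled for All LEN, places Baseline on or before the First Dose Date, without saying which of the two.

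The operative rules use neither defined term:

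- **SAP 3.8.3, general baseline:** "the last nonmissing value with collection date (and time, if available) on or prior to the first dose date (and time) of study drug", subject to anything specified otherwise.
- **SAP 3.8.3, baseline HIV-1 RNA:** the latest "record(s) on or prior to the first dose date and time of study drug will be selected", with no such proviso.
- **SAP 7.2.1, laboratory baseline:** "the last measurement obtained on or prior to the date of first dose of study drug".
- **SAP 7.3, body weight and vital signs:** the same anchor.
- **SAP 7.1.5.1:** "The TEAEs are defined as any AEs that begin on or after the date of first dose of study drug".
- **SAP 7.1.5.2:** incomplete adverse-event dates are compared with the first dose date of study drug.

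Under Protocol 3.2, Cohort 1B takes placebo from Day 1 and its first LEN dose on Day 15.

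**The concern.** The two first dose dates coincide in Cohorts 1A and 2 and differ only in Cohort 1B. There, a programmer who follows the study-drug wording takes the Day 1 pre-placebo value as baseline while counting visits from Day 15, and flags events that began on placebo as treatment-emergent. A programmer who follows SAP 3 and the All LEN date does neither. Both can say that they followed the SAP.

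At stake are the Cohort 1 and total columns of the LEN tables. With the earlier baseline, change in HIV-1 RNA and CD4 count takes in 14 days on placebo. A laboratory grade increase that arose on placebo and persisted is counted as emergent on LEN. Participants may also fall in a different baseline viral-load or CD4 subgroup. By default, SAP 3 presents results by cohort and total, so no placebo column would keep placebo-period events apart.

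**Working it through.** **1. Which first dose Table 3-1 counts from.** With the first oral LEN dose as origin, the nominal day is 1 + 14 + 7 × week. This gives Day 1 SC = 15, Week 4 = 43, Week 26 = 197, Week 104 = 743 and Week 156 = 1107, as printed. All 20 rows from Day 1 SC to Week 208 reproduce. With the placebo dose as origin, Cohort 1B would need 1 + 28 + 7 × week, which gives 29, 57, 211, 757 and 1121 for the same rows. None of the 20 matches. The table runs from the first LEN dose.

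**2. Cohort 1B records under both rules.** By SAP 3.8.1, Study Day before the first dose is the date difference; from the first dose on, it is the difference plus 1.

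| Cohort 1B record | All LEN Study Day | Table 3-1 window (All LEN date) | Status under the 3.8.3 wording |
|---|---|---|---|
| Day 1 predose | 1 − 15 = −14 | Baseline | Baseline |
| Day 2 | 2 − 15 = −13 | Baseline | Postbaseline |
| Day 8 | 8 − 15 = −7 | Baseline | Postbaseline |
| Day 15 predose | 15 − 15 + 1 = 1 | Baseline | Postbaseline |

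The same Day 15 record is the baseline under one rule and a postbaseline value under the other.

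**3. Whether a LEN baseline exists.** Protocol Appendix 2 schedules HIV-1 RNA, CD4 count, laboratory tests and vital signs on Day 15 for Cohort 1B. Protocol 6.3.2 gives the LEN dose after the Day 15 assessments.

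**4. How many participants.** Cohort 1 has 36 participants randomized 2:1 (SAP 1.2), so 36 × 1/3 = 12 on placebo. That is 12/36 = 33% of Cohort 1 and 12/72 = 17% of the 72 enrolled (Protocol 1.2.2.2), if all go on to LEN. Placebo time is 12 × 14 = 168 participant-days. One participant wrongly counted adds 1/72 = 1.4 points to the total column or 1/36 = 2.8 points to the Cohort 1 column. The addition is zero if that participant also qualifies for the same row while on LEN.

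**5. How far the HIV-1 RNA baselines might differ.** The sample size section (Protocol 8.9, SAP 1.3) assumes that 10% of placebo participants fall by at least 0.5 log10. Applied to 12 independent participants, the expected number is 12 × 0.10 = 1.2, and the chance of at least one is 1 − 0.9^12 = 0.72. This is a planning assumption, not an observed rate.

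**6. What is not exposed.** The snapshot uses absolute thresholds and no baseline value, and SAP 6.2.1 counts Study Day from the first oral LEN dose. Even from the placebo origin the scheduled visits stay in their windows: Week 104 is day 743 or 757 (window 688 to 778), and Week 156 is day 1107 or 1121 (window 1052 to 1142). SAP 6.1 places the primary endpoint under the Week 26 SAP.

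**The case against.** The strongest reply is that the SAP's intent is clear. All LEN has its own first dose date, the Baseline row stands in the All LEN table, the general baseline rule yields to other specifications, and SAP 3 limits the analysis to data from the first LEN dose on. SAP 7.1.6.1 ties the high-level adverse-event summary to All LEN. Much of this stands: the first LEN dose is the likely intention, and SAP 3 would remove most placebo-period events.

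It does not close the gap. The HIV-1 RNA baseline rule and SAP 7.1.5.1, 7.2.1 and 7.3 carry no proviso. SAP 3 settles which data enter, not which predose record is the baseline; taken literally it would also shut out predose baselines taken on earlier days. A grade increase that persists beyond Day 15 passes the SAP 3 filter and is still judged against a Day 1 value. Elsewhere the SAP names LEN when it means LEN (4.3, 6.2.1, Appendix 3 item 8).

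Two further points for the other side also stand. The adverse-event wording follows Protocol 8.6.2, so narrowing it is a change from the protocol. Protocol 6.7.1 does use "Day 15 for Cohort 1B participants" as the reference for suboptimal response, but for managing virologic failure; it does not set the statistical baseline.

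A reader might infer that preferred-term rates could be inflated by several points. Five of the 12 would give 5/72 = 6.9 points, but only if five placebo participants had the same preferred term within 14 days and none had it again on LEN. The documents give no placebo-period event rate to support that.

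**Conclusion.** The inconsistency is real and confined to Cohort 1B. Followed literally, the stated rules give that arm a baseline 14 days too early for an All LEN analysis, and make placebo-period events and grade increases emergent in LEN tables.

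A reader might go further and conclude that the SAP has adopted a wrong baseline, or that the efficacy conclusions are at risk. The documents support neither. Other passages point to the first LEN dose, and the overall Week 104 and 156 snapshot results and the primary endpoint do not depend on the conflicting rules.

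The exposed outputs are descriptive: change from baseline in HIV-1 RNA, CD4 count, laboratory values and vital signs; the baseline viral-load and CD4 subgroups; treatment-emergent laboratory grades; and adverse-event counts. The size is up to 1.4 points (of 72) or 2.8 points (of 36) per participant wrongly counted. The total cannot be stated from the documents. The figures assume exact 2:1 allocation and that all 12 placebo participants went on to LEN. The text should be corrected, but the problem does not threaten the main results.

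**What to change.** - In SAP 3.8.3 (both baseline rules), 7.1.5.1, 7.1.5.2, 7.2.1 and 7.3, state that for All LEN analyses the first dose is the First Dose Date for All LEN Analysis. Baseline in Cohort 1B is then the last value before the first LEN dose, normally Day 15 predose.
- SAP 7.2.2.1 needs no replacement of its own, because it refers only to baseline. Add that it inherits this one.
- Keep the Day 1 baseline, before randomized treatment, for the Cohort 1 LEN-versus-placebo comparisons in SAP 5.1 and 5.2. A blanket replacement would give the placebo group a post-randomization baseline there.
- Keep placebo-period events in the listings.
- Revise SAP 7.8, which now declares no change from the protocol's safety analyses, to record the narrower adverse-event definition against Protocol 8.6.2.

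The cost is SAP wording, a declared departure from the protocol, and a check of which date the programs use for Cohort 1B. No new data are needed, since the Day 15 assessments are already scheduled.
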